**Table 5-1 Recommended minimum daily dietary allowances (Ross 2011)**

Age	Vitamin D	Calcium
≥ 5 years to ≤ 8 years	600 IU	1000 mg
≥ 9 years to ≤ 17 years	600 IU	1300 mg

All patients should take at least 600 IU vitamin D daily from Visit 1 until the final Visit through diet and/or supplementation.

Elemental calcium, at least 1000 mg for 5-8 years of age or at least 1300 mg for 9-17 years of age, daily will be taken beginning at Visit 1 and during the total duration of the trial, through diet and/or supplementation. Calcium carbonate is the preferred form of calcium supplementation. If calcium carbonate is not well tolerated, another form of oral calcium would be acceptable.

Any vitamin D and calcium supplements will be recorded on the Concomitant medications/Significant non-drug therapies (e)CRF.

In addition, transient hypocalcemia has been reported especially following the first infusion and it can cause symptoms in rare cases. To prevent the development of symptomatic hypocalcemia, the parent or guardian of each child will receive an information sheet and all patients will receive calcium supplementation at the doses recommended in [Table 5-1](#) starting from the day of infusion and for a minimum of 5 days after each infusion (for sites where this calcium supplementation usually starts prior to the infusion, the total treatment period is approximately 10 days in total) ([Hogler et al 2004](#)).

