### Schwartz Formula to calculate Glomerular Filtration

$$\text{GFR (mL/min/1.73 m}^2\text{)} = k [\text{Height (m)}] / \text{Serum Creatinine (mg/dL)}$$

k = Constant

k=0.41

Additional renal and calcium monitoring will be performed 10 days after each study drug infusion (Visit 3 and Visit 6).

Local laboratory evaluation of serum creatinine will be performed at Visits 1 and 2, if there is an increase greater than 0.5 mg/dL (44.2  $\mu\text{mol/L}$ ), the patient should be excluded.

Serum ionized calcium will be evaluated in the local laboratory at pre-dose (first infusion). If the result is close to or below the lower limit of the normal range, the infusion must be delayed until the value has returned to normal.

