## 7 Safety monitoring

### 7.1 Adverse events

An adverse event (AE) is any untoward medical occurrence (e.g., any unfavorable and unintended sign [including abnormal laboratory findings], symptom or disease) in a subject or clinical investigation subject *after providing written informed consent* for participation in the study until the end of study visit. Therefore, an AE may or may not be temporally or causally associated with the use of a medicinal (investigational) product.

In addition, all reports of intentional misuse and abuse of the product are also considered an adverse event irrespective if a clinical event has occurred.

In this protocol, due to the long screening period (at least 4 weeks), although SAEs are collected from signing the informed consent, the AE page of the eCRF is only completed from the first day of study drug. In the case of randomized patients only, any events that occur prior to receiving study treatment, should be recorded in the eCRF as Medical History.

The occurrence of adverse events must be sought by non-directive questioning of the patient at each visit during the study. Adverse events also may be detected when they are volunteered by the patient during or between visits or through physical examination findings, laboratory test findings, or other assessments.

Abnormal laboratory values or test results constitute adverse events only if they fulfill at least one of the following criteria:

- they induce clinical signs or symptoms,
- they are considered clinically significant,
- they require therapy.

Clinically significant abnormal laboratory values or test results must be identified through a review of values outside of normal ranges/clinically notable ranges, significant changes from baseline or the previous visit, or values which are considered to be non-typical in patient with underlying disease. Investigators have the responsibility for managing the safety of individual patient and identifying adverse events. Alert ranges for laboratory and other test abnormalities are included in [Appendix 1](#).

Adverse events must be recorded in the Adverse Events CRF under the signs, symptoms or diagnosis associated with them, accompanied by the following information:

- the severity grade
  - mild: usually transient in nature and generally not interfering with normal activities
  - moderate: sufficiently discomforting to interfere with normal activities
  - severe: prevents normal activities

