Adverse events associated with change in renal function are defined based on predefined search list which describe a clinically significant change in renal function. A search of the clinical trial database will occur based on this pre-specified list of MedDRA preferred terms. These adverse events will be summarized by preferred term. In addition, the event rate and 25th percentile (95% CI) of time to first adverse event associated with change in renal function will be summarized. The hazard ratio and 95% CI based on a Cox proportional hazards model with treatment as a factor will be presented. Between-treatment differences in time to first adverse event associated with change in renal function will be evaluated using the log-rank test. If a patient experiences an adverse event associated with change in renal function, the event time is defined as the earliest of all events if there are multiple. Otherwise, a patient is considered censored at the last contact date. Kaplan-Meier estimates will be plotted over time if at least 1% of overall population has experienced the event.

Patient listings will be provided for all adverse events associated with clinically significant change in renal function.

Hypocalcaemia adverse events and laboratory events

Hypocalcaemia adverse events will be searched based on preferred term and summarized. Patients with reported laboratory measurements associated with a signal of hypocalcaemia will be summarized by visit. Lab hypocalcaemia (low serum calcium levels) is present if the value of serum calcium from central lab is less than the lower limit of normal range provided by the central lab.

The number and percentage of patients who met these criteria will be summarized by treatment group overall.

The event rate and 25th percentile (95% CI) of time to first hypocalcaemia occurrence based on AE and central lab calcium will be summarized. The hazard ratio and 95% CI based on a Cox proportional hazards model with treatment as a factor will be presented. Between-treatment differences in time to first hypocalcaemia occurrence based on AEs and central lab will be evaluated using the log-rank test. If a patient experiences a hypocalcaemia and low calcium value based on the central lab, the event time is defined as the earlier of these events. Otherwise, a patient is considered censored at the last contact date. Kaplan-Meier estimates will be plotted over time if at least 1% of overall population has experienced the event.

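### Read literally, the time-to-first-hypocalcaemia rule counts only children with both an adverse event and a low central calcium; the SAP should say that either one counts

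*SAP*

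**What the plan says.** The SAP section on hypocalcaemia adverse events and laboratory events names the endpoint: "time to first hypocalcaemia occurrence based on AE and central lab calcium will be summarized". It defines the laboratory component on its own: "Lab hypocalcaemia (low serum calcium levels) is present if the value of serum calcium from central lab is less than the lower limit" of the central laboratory's normal range. The event rule follows: "If a patient experiences a hypocalcaemia and low calcium value based on the central lab, the event time is defined as the earlier" of the two. The next sentence reads: "Otherwise, a patient is considered censored at the last contact date".

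The event rate, the 25th percentile, the Cox hazard ratio, the log-rank test and the Kaplan-Meier plot all use this rule. The list of adverse event outputs in the SAP again joins the two sources with *and*. The SAP nowhere says that one source is enough.

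On the clinical setting, Protocol 5.1.2 states that "transient hypocalcemia has been reported especially following the first infusion", with symptoms only rarely. On sampling, Protocol 6.5.4.2 says: "Additional renal and calcium monitoring will be performed 10 days after each study drug infusion (Visit 3 and Visit 6"). Protocol 6.5.4 adds central chemistry at screening, Month 6 and Month 12.

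**The concern.** The condition joins two findings with *and*, and the next sentence censors whoever does not meet it. A programmer who follows the text would treat two kinds of affected child as event-free: one with a hypocalcaemia adverse event but no low central value, and one with a low central value but no adverse event.

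Hypocalcaemia after infusion is a named safety concern here. The rationale for Amendment 5 records the monitoring committee's concern about it and adds calcium supplementation around the infusion in response. A time-to-event display that counts only the overlap of two sources would show a lower incidence than the data hold.

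**Working it through.** **1. Plan figures.** The documents give no hypocalcaemia rate, event count or power, so there is no plan figure to reproduce for this endpoint. The sample size section only fixes the scale: 82 / (1 − 0.10) = 91.1, rounded up to 92, or 46 per arm.

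**2. The rule applied to each kind of child.**

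| Child has | Rule as written | Either-source rule |
|---|---|---|
| Adverse event and low central calcium | Event at the earlier date | Same |
| Adverse event only | Censored at last contact | Event at adverse event date |
| Low central calcium only | Censored at last contact | Event at sample date |
| Neither | Censored at last contact | Same |

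**3. Whether the two middle rows are realistic.**
- *Laboratory only.* Protocol 7.1: "Abnormal laboratory values or test results constitute adverse events only if they fulfill at least one of the following criteria". The criteria are signs or symptoms, clinical significance, or need for therapy. A low value without symptoms therefore need not become an adverse event.
- *Adverse event only.* After the first infusion, central calcium is first scheduled at Day 10. A transient symptomatic episode can resolve before then. How often this happens is not documented.

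**4. Size, under assumed rates.** Let *a* be the risk of an adverse event, *l* the risk of a low central value and *b* the risk of both. Affected children are *a + l − b*, the written rule counts *b*, and the share lost is 1 − *b*/(*a + l − b*). With 92 children:

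| Assumed *a*, *l* | Overlap | Affected | Counted | Lost |
|---|---|---|---|---|
| 5%, 10% | none | 13.8 | 0 | 100% |
| 5%, 10% | half of adverse events | 11.5 | 2.3 | 80% |
| 5%, 10% | all adverse events | 9.2 | 4.6 | 50% |
| 5%, 20% | all adverse events | 18.4 | 4.6 | 75% |
| 15%, 20% | all adverse events | 18.4 | 13.8 | 25% |
| 10%, 10% | complete | 9.2 | 9.2 | 0% |

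More than half are lost whenever fewer than half of the affected children have both components.

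**5. Precision and the hazard ratio.** Assume either-source risks of 25% on zoledronic acid and 8% on placebo, with 46 per arm.
- All affected children counted: 46 × 0.33 = 15.2 events, hazard ratio ln(0.75)/ln(0.92) = 3.45, and about 67% power by Schoenfeld's formula.
- A quarter in each arm have both: risks 6.25% and 2%, 3.8 events, hazard ratio 3.19, about 20% power. The ratio changes little, but precision falls sharply.
- Half on zoledronic acid and a quarter on placebo have both: 12.5% and 2%, hazard ratio ln(0.875)/ln(0.98) = 6.61.
- A quarter on zoledronic acid and half on placebo have both: 6.25% and 4%, hazard ratio ln(0.9375)/ln(0.96) = 1.58.

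The hazard ratio can therefore move either way.

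**6. Plot threshold.** The Kaplan-Meier plot needs events in at least 1% of the population: 0.01 × 92 = 0.92, so one child is enough. If no child had both components, there would be no plot, even with several affected children.

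**7. Timing.** Take a child with low calcium on Day 10 and a hypocalcaemia adverse event on Day 200. The written rule records an event at Day 10. If the same child's last contact is Day 150, before any adverse event, the child is censored at Day 150. Event status at Day 10 then depends on what happens afterwards, which a time-to-event analysis should not allow.

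**The case against.** The strongest reply is that the either-source meaning is evident. The section heading names adverse events and laboratory events side by side, laboratory hypocalcaemia is defined without an adverse event, and the endpoint is a first occurrence. Timing at the earlier of the two treats each as an event in its own right. The renal rule just above it has a similar shape: one qualifying adverse event is enough, and several are resolved by taking the earliest. On that reading the calcium sentence is only a tie-break for children with both.

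This supports the likely intent, but it does not repair the text. The renal rule makes any single event qualify; the calcium rule turns the tie-break into the entry condition and sends everyone else to censoring.

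Three further objections stand as limits:
- Every detected case still appears elsewhere: the adverse event table by preferred term, laboratory hypocalcaemia by visit, newly occurring hypocalcaemia, and the listings.
- Overlap could be high. Protocol Appendix 1 classes any calcium outside the normal range as a clinically significant change, to be recorded as medical history, an adverse event or a serious adverse event. Applied strictly, many low post-dose values would also be adverse events.
- An asymptomatic dip that resolves before Day 10 is missed under either rule.

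A reader might infer that the sponsor chose a both-sources endpoint, that most events will be lost, or that the hazard ratio for zoledronic acid will be biased downwards. The documents support none of these: the intent is open, no rates or overlap are given, and the direction depends on how overlap differs between arms.

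**Conclusion.** The wording is defective and should be corrected. As written, the rule censors children with only one of the two findings, and no other text overrides it, although the sentence itself hints that either was meant to count.

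If programmed literally, it would understate hypocalcaemia incidence in the time-to-event outputs whenever single-source cases occur, reduce precision, and let event status depend on later findings. The effect on the hazard ratio has no known direction. The size of the loss is not derivable: the 0% to 100% range rests entirely on assumed risks and overlaps. Only the time-to-event outputs are affected.

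**What to change.** Replace the event and censoring sentences in the SAP with:

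> If a patient has a treatment-emergent hypocalcaemia AE, or a post-baseline central-lab calcium below the lower limit of normal, or both, the event time is the date of the earliest of these. A patient with neither is censored at the last contact date.

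*Post-baseline* is needed because Table 6-1 allows an optional repeat central sample at Visit 2, and a low pre-dose value should not count as an event.

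The cost is one sentence and a check that the program matches it; no new data are needed. The combined endpoint will mix clinical events with laboratory findings without symptoms, so it should be read beside the separate adverse event and laboratory tables already planned. Settle the wording before unblinding, so that a safety endpoint is not defined after results are seen.

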		> 7- 10 yrs/ Female	(0.2, 0.6)	Outside the normal range
		> 10 - 13 yrs/ Female	(0.3, 0.7)	Outside the normal range
		> 13 - 16 yrs/ Female	(0.4, 0.8)	Outside the normal range
		> 16 - 17 yrs/ Female	(0.5, 0.9)	Outside the normal range
		5 - 7 yrs/ Male	(0.2, 0.5)	Outside the normal range
		> 7- 10 yrs/ Male	(0.3, 0.6)	Outside the normal range
		> 10 - 13 yrs/ Male	(0.3, 0.7)	Outside the normal range
		> 13 - 16 yrs/ Male	(0.4, 0.8)	Outside the normal range
		> 16 - 17 yrs/ Male	(0.5, 0.9)	Outside the normal range

Laboratory parameter	Units	Age/gender range	Normal range	Criteria for clinically significant change
Magnesium	mg/dl	5 - 7 yrs/ Female	(1.7, 2.2)	Clinically significantly low, if < 1.0 mg/dL
		> 7- 10 yrs/ Female	(1.6, 2.2)	Clinically significantly low, if < 1.0 mg/dL
		> 10 - 13 yrs/ Female	(1.6, 2.2)	Clinically significantly low, if < 1.0 mg/dL
		> 13 - 16 yrs/ Female	(1.6, 2.3)	Clinically significantly low, if < 1.0 mg/dL
		> 16 - 17 yrs/ Female	(1.5, 2.2)	Clinically significantly low, if < 1.0 mg/dL
		5 - 7 yrs/ Male	(1.7, 2.4)	Clinically significantly low, if < 1.0 mg/dL
		> 7- 10 yrs/ Male	(1.6, 2.2)	Clinically significantly low, if < 1.0 mg/dL
		> 10 - 13 yrs/ Male	(1.6, 2.2)	Clinically significantly low, if < 1.0 mg/dL
		> 13 - 16 yrs/ Male	(1.6, 2.3)	Clinically significantly low, if < 1.0 mg/dL
		> 16 - 17 yrs/ Male	(1.5, 2.2)	Clinically significantly low, if < 1.0 mg/dL
Potassium	mEq/L	> 1 - 17 yrs	(3.4, 5.4)	Outside the normal range
Phosphorus	mg/dl	5 - 10 yrs	(3.2, 6.1)	Outside the normal range
		> 10 - 15 yrs	(3.1, 6.0)	Outside the normal range
		> 15 - 17 yrs	(2.2, 5.1)	Outside the normal range
Sodium	mEq/L	≤ 17 yrs	(132.0, 147.0)	Outside the normal range
Hemoglobin	g/dl	5 - 12 yrs/ Female	(11.2, 15.5)	Outside the normal range
		> 12 - 17 yrs/ Female	(11.6, 16.4)	Outside the normal range
		5 - 12 yrs/ Male	(11.2, 15.5)	Outside the normal range
		> 12 - 17 yrs/ Male	(12.7, 18.1)	Outside the normal range
ALT	u/L	5- 17 yrs	( 6 , 200 )	Outside the normal range
AST	u/L	5- 17 yrs	(10 , 200 )	Outside the normal range
Alkaline Phosphatase	u/L	5- 17 yrs	( 51 , 315)	Outside the normal range
Albumin	g/dL	5- 17 yrs	( 2.9 – 4.7 )	Outside the normal range
Hematocrit	%	5- 6 yrs/ Female	(35.0, 44.0)	Outside the normal range
		> 6 - 12 yrs/ Female	(34.0, 44.0)	Outside the normal range

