## 15 Appendix 3: Amount of blood to-be Drawn

Period	Screen	Treatment						
Visit	1	2	3	4 T	5	6	7 T	8 and TD and/or PSW
Day	-28	1	10	90	180	190	270	365
Week	-4			12	26		39	52
Central Laboratory - All Patients								
Hematology	3 mL				3 mL			3 mL
Chemistry	3.5 mL [6 mL (Australia only)]				3.5 mL			3.5 mL [6 mL (Australia only)]
Renal & Ca monitoring 			3.5 mL			3.5 mL		
Serum pregnancy 	2.5mL							2.5mL
Specialized serum bone-markers		3 mL			3 mL			3 mL
Vitamin D	2.5 mL							2.5 mL
Local Laboratory - All Patients								
Serum creatinine	2.5 mL	2.5 mL						
Serum ionized calcium		2.5 mL						
TOTALS	14 mL [16.5mL (Australia only)]	8 mL	3.5mL	-	9.5mL	3.5mL	-	14.5 mL [17.0mL (Australia only)]
 Serum creatinine, urea, electrolytes, calcium, magnesium, phosphorus only								
 Only in girls of child bearing potential								

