Patient listings will be provided for all adverse events associated with hypocalcaemia.

Laboratory parameters

The summary of laboratory evaluations will be presented with respect to three groups of laboratory tests (hematology, serum chemistry, and urinalysis).

- Hematology parameters: hemoglobin, hematocrit, red blood cell count, white blood cell count with differential counts, and platelet count.
- Serum chemistry parameters: non-fasting glucose, creatinine, serum urea, uric acid, total protein, SGOT (AST), SGPT (ALT), alkaline phosphatase, sodium, potassium, chloride, phosphorus, magnesium, albumin, calcium; and Glomerular Filtration Rate (GFR).
- Urinalysis parameters: amorphous crystals, urine bilirubin, urine blood, calcium oxalate crystals, urine color, urine glucose, urine ketone, urine leukocytes, urine nitrite, pH, urine protein dipstick, specific gravity, urine urobilinogen, and WBC Casts (Urine) /LPF.

GFR will be calculated using the Schwartz equation at all visits where serum creatinine will be measured (Visits 1, 3, 5, 6 and 8) by the Central Laboratory.

$$\text{GFR (mL/min/1.73 m}^2\text{)} = k[\text{Height (m)}]/\text{Serum Creatinine (mg/dL)}, \text{ where } k=0.41$$

Descriptive summary statistics for baseline, each post-baseline visit, and change from baseline to each visit will be presented by laboratory test group and treatment group. Note that if either the baseline or the post-baseline value is missing, then the calculation of change from baseline will also be missing.

Also, shift tables for hematology and serum chemistry will be provided in order to compare a patient's baseline laboratory evaluation relative to each study visit. For the shift tables, the normal laboratory values will be used to evaluate whether a particular laboratory test value is normal, low, or high for each visit value relative to whether or not the baseline value is normal, low, or high. These summaries will be presented by laboratory test group and treatment group.

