In addition, a summary table will be presented for the incidence rates of newly occurring clinically notable laboratory abnormalities, where patients will be counted if they have normal or missing baseline value and with at least one post-baseline assessment satisfying the clinically notable criteria. Incidence rates of newly occurring hypocalcaemia (based on central lab) by visit will be summarized similarly for patients who have normal or missing baseline level of serum calcium and clinically notable abnormal serum calcium level at each scheduled post-baseline visit. The definition of clinically notable laboratory abnormalities can be found in Appendix section "Clinically notable laboratory values and vital signs" in the protocol.

Furthermore, a summary table will be provided for the number and percentage of patients with liver enzyme abnormalities by each study visit and with at least one post-baseline assessment satisfying the liver enzyme abnormalities.

Listings of all laboratory parameter measurements will be displayed. In addition, listings of hematology and biochemistry assessments will be provided for patients with newly occurring clinically notable laboratory abnormalities. In these listings, all laboratory values will be

displayed for any patient who has at least one newly occurring clinically notable laboratory abnormality. The abnormal value will be flagged, e.g., L/H for a value being below/above normal range, and the lower and upper limit of normal values will be presented as well. Central lab calcium values will also be listed for patients with at least one post-baseline laboratory signal of hypocalcaemia and the below normal serum calcium results will be flagged as L.

For each numerical laboratory parameter, the number of decimal places to be used for laboratory values should be the same as that for the normal range. For continuous variables recorded as <lower limit>, these will be imputed as being half of the lower limit.

All laboratory parameters will be expressed using SI units.

Vital signs, [REDACTED] and weight

Descriptive summary statistics for the baseline, each study visit, and change from baseline to each study visit will be presented for sitting systolic blood pressure, sitting diastolic blood pressure, pulse rate, and body weight. [REDACTED]

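### The newly occurring notable laboratory table requires a normal baseline rather than one not already notable in the same direction, so it omits some first notable values, chiefly for magnesium

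*SAP*

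**What the plan says.** The SAP section on laboratory parameters plans a table of incidence rates of newly occurring clinically notable abnormalities, in which "patients will be counted if they have normal or missing baseline value and with at least one post-baseline assessment satisfying the clinically notable criteria". For the criteria it points to the protocol: "The definition of clinically notable laboratory abnormalities can be found in Appendix section" on clinically notable values, which is Protocol Appendix 1. A companion output has the same restriction: "listings of hematology and biochemistry assessments will be provided for patients with newly occurring clinically notable laboratory abnormalities". A by-visit table of newly occurring hypocalcaemia also requires a normal or missing baseline calcium.

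In Appendix 1 nearly every laboratory parameter is notable when it lies outside the normal range on either side. Magnesium is the exception: "Clinically significantly low, if < 1.0 mg/dL". Its lower normal limit is 1.5, 1.6 or 1.7 mg/dL depending on age and sex.

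Other SAP outputs carry no baseline restriction. Shift tables for hematology and serum chemistry assess "whether a particular laboratory test value is normal, low, or high for each visit value relative to whether or not the baseline value" falls in the same categories. The hypocalcaemia section says "Patients with reported laboratory measurements associated with a signal of hypocalcaemia will be summarized by visit", with low calcium defined as below the central laboratory's lower limit. Finally, "Listings of all laboratory parameter measurements will be displayed".

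**The concern.** A newly notable value should be one that is notable now and was not notable in that direction at baseline. The SAP substitutes a normal baseline. The two rules agree when the baseline is in range. They differ in two situations.

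- **Abnormal but not yet notable.** This arises where the notable threshold lies beyond the normal limit, which in Appendix 1 is the case for magnesium.
- **Out of range on one side, later out of range on the other.** The later value is new in its direction, but the child was removed from the count at baseline.

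Magnesium is not an incidental analyte here. The post-infusion draws at Visits 3 and 6 cover "Serum creatinine, urea, electrolytes, calcium, magnesium, phosphorus only" (Protocol Appendix 3, footnote 1). Nor does eligibility remove children with low magnesium: exclusion criterion 5 covers low calcium and low phosphorus at screening and does not mention magnesium. At stake is whether a table offered as incidence of new laboratory abnormalities counts the events its title describes.

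**Working it through.** The documents state no figure to reproduce, so the check applies the counting rule to cases.

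**Inputs (Protocol Appendix 1).** Magnesium: lower normal limit 1.5 to 1.7 mg/dL; notable below 1.0 mg/dL; range 1.6 to 2.2 for girls over 7 to 10 years. Potassium: 3.4 to 5.4 mEq/L. Calcium: 8.4 to 10.3 mg/dL. WBC, over 6 to 12 years: 4.35 to 13.65 (10³/µL). The last three are notable when outside the range.

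**Magnesium band.** Baselines that are abnormal but not notable run from 1.0 up to the lower limit. The width is lower limit − 1.0:
- 1.5 − 1.0 = 0.5 mg/dL at the narrowest;
- 1.7 − 1.0 = 0.7 mg/dL at the widest.

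**Rules compared.**
- SAP: baseline normal or missing, and notable after baseline.
- Rule A: baseline not notable, and notable after baseline.
- Rule B: notable after baseline in one direction, and baseline not notable in that same direction.

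The values below are illustrative.

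| Baseline to later value | Shift cell | SAP | Rule A | Rule B |
|---|---|---|---|---|
| Magnesium 1.8 to 0.8 | normal to low | counted | counted | counted |
| Magnesium 1.3 to 0.8 | low to low | omitted | counted | counted |
| Magnesium 2.4 to 0.8 | high to low | omitted | counted | counted |
| Potassium 3.2 to 5.8 | low to high | omitted | omitted | counted |
| Calcium 10.6 to 7.9 | high to low | omitted | omitted | counted |
| WBC 15 to 3.5 | high to low | omitted | omitted | counted |
| Calcium 8.2 to 7.0 | low to low | omitted | omitted | omitted |

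**Reading the table.** Rule A repairs magnesium only. Side-crossing needs the direction in rule B. The last row shows that rule B does not over-correct: a child already low stays out of the low count.

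**Where the omitted cases appear instead.** The potassium, calcium and WBC crossings each fall in their own shift-table cell, and the calcium case also enters the hypocalcaemia analyses. Magnesium 1.3 to 0.8 shares its cell with a child who stays at 1.3 throughout. It can be seen only in the all-values listing and, indirectly, in by-visit summaries such as the minimum. No table marks it as notable.

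**Hypocalcaemia table.** It borrows the Appendix 1 calcium criterion, which is two-sided, although its subject is low calcium. The SAP's own hypocalcaemia section uses only the lower limit. Stating the low direction would align the two.

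**The case against.** The strongest reply is that the plan has several laboratory outputs and this table is only one of them. A reader might infer from the counting rule that these children are never counted anywhere. The documents do not support that. The shift tables have no baseline restriction and show side-crossing by arm and visit. The hypocalcaemia summaries state no baseline condition. Every value is listed, and Protocol section 7.1 has investigators review abnormal values for clinical significance as adverse events. This stands, with two limits: the shift tables work visit by visit and give no count of children with at least one event, and they cannot separate the magnesium case.

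A reader might also take this table to be the plan's main summary of laboratory harm. It is not presented so. The SAP adds it after the descriptive summaries and shift tables, and Protocol section 9.5.2.2 promises only those two.

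It is tempting to assume a prevalence of out-of-range baselines and turn it into a number of children lost. The documents give no baseline laboratory distribution. Such a figure would also not measure missed events, because a child with an abnormal baseline is missed only on crossing to the other side or, for magnesium, on falling below 1.0.

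Counting a missing baseline as new might look like a further error. It can only add events, which is a defensible conservative choice in a safety table, and it should be rare because the Visit 1 results are due before Visit 2.

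Finally, low calcium or phosphorus at screening is an exclusion. For those two, a low baseline could arise only from the optional repeat at Visit 2.

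**Conclusion.** The point holds for the newly occurring notable table, its listing and the newly occurring hypocalcaemia table. The magnesium gap is the substantive part: a first value below 1.0 mg/dL from a baseline in a band 0.5 to 0.7 mg/dL wide is labelled notable in no table. Side-crossing is a lesser gap, since other outputs show it.

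The conclusion assumes that a normal baseline means one within the normal range, which is how the shift tables in the same SAP section use the word. If it was meant as not notable, the magnesium gap closes but side-crossing remains omitted, and the SAP would need to say so.

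The impact is on descriptive safety reporting only and does not touch the primary analysis. How many children are affected cannot be derived from the documents. Severity: minor.

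**What to change.** In the SAP, define newly occurring separately for low and high: at least one post-baseline value meets the Appendix 1 notable criterion in that direction, and the baseline value did not meet it in that same direction. The present handling of missing baselines can stay. State as denominator the children at risk in that direction. Use the same definition for the accompanying listing, and apply the low-direction rule to the newly occurring hypocalcaemia table. The Appendix 1 thresholds are unchanged.

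The cost is one SAP sentence and one programming flag, with no new data. The small downside is that the table splits into low and high.
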